9.2 SETTING

9.2.1 Definitions

Study Period: the entire period of time that includes the baseline period, the cohort entry date (index date), and follow-up period for the study population. The study period will be from **01 April 2015** (180 days prior to Spiolto approval date of 28 September 2015 in Japan) to **31 March 2019** (end of available data).

Patient Selection Period: the period of time for which patients are eligible to enter the cohort. The earliest date of the patient selection period is **28 September 2015**, (the Spiolto approval date in Japan). The latest date of the patient selection period is 31 December 2018, corresponding to 90 days before the end of available data (31 March 2019), ensuring that all patients have at least 60 days after the cohort entry date to identify a second prescription for index therapy and at least 30 days to be capable of the 30-day overlap to determine the triple therapy initiation outcome.

Cohort Entry Date: Date of entry to the initial cohort of Tio/Olo vs. Tio users (*first prescription*).

Baseline Period: the 180-day period that ends 1 day prior to the cohort entry date used to assess covariate information. The earliest start of the baseline period would be 01 April 2015, corresponding to 180 days prior to the approval date of Spiolto.

[figure not shown]
Follow-Up Period: the period starting at the second prescription for Tio/Olo or Tio within 60 days of the cohort entry date (first prescription) and ending at the earliest occurrence of the outcome (use of triple therapy), or the first occurrence of inpatient death, disenrollment, or end of the study period (31-Mar-2019). A sensitivity analysis will employ an as-treated censoring approach to further censor upon discontinuation of index therapy or initiation of the other index treatment arm. Patients may have different lengths of follow-up (i.e. variable follow-up).

Since health care is nationalized in Japan, the notion of enrollment is not applicable. Therefore, a proxy enrolment criterion defined as start of enrolment = date of first inpatient/outpatient encounter; end of enrolment = date of last inpatient/outpatient encounter will be used. “Enrolment” herein will refer to this proxy enrolment measure. For entry into the study population, patients will be required to have had at least 180 days of enrollment prior to the cohort entry date.

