9.3.2.2 Secondary outcomes and further endpoints

Secondary outcomes

- Time to First Moderate or Severe COPD Exacerbation
 - Time to First Moderate COPD Exacerbation
 - Time to First Severe COPD Exacerbation
- Number of Moderate or Severe COPD Exacerbations
 - Number of Moderate COPD Exacerbations
 - Number of Severe COPD Exacerbations

Further endpoints:

- All-Cause Inpatient Mortality
- Number of Unique Pulmonary Medications
- Number of Hospitalizations for a Respiratory Condition
- Major Cardiovascular Adverse Events (MACE)
- Home oxygen therapy (HOT)

Moderate exacerbations will be defined as an outpatient visit with a diagnosis code for COPD in any field + a prescription for an oral corticosteroid or an antibiotic for respiratory infections,. Severe

exacerbations will be defined as a hospitalization with a primary diagnosis for COPD. (**Chatterjee 2012**)

Unique pulmonary medications will be defined as the following treatments: LAMA, LABA, SAMA, SABA, inhaled/oral glucocorticoids, systemic glucocorticoids, antileukotriene agents, biologics (anti-IgE, anti-IL-5, anti-IL-4), allergy medications, xanthines (theophylline), and mycolytics.

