9.3.3 Covariates

The covariates listed below consist of demographics, medications, comorbidities, and other variables that are hypothesized to confound the relationship between exposure and outcome. Covariates will be identified based on data recorded within 180 days prior to or on the index date (date of

dispensing/initiation of the exposure), unless otherwise specified. If multiple measurements are made in the baseline period, then the most recent measurement will be used.

There is an additional variable for “doubt diagnosis” related to each disease diagnosis. Only confirmed diagnoses will be used for all disease variables (this represents ~95% of all diagnoses).

Absolute and relative frequencies of each covariate will also be reported. Detailed descriptions of the listed covariates can be found in Annexes 2 and 3. The measure definitions for diagnoses are subject to modification to further incorporate disease codes/names as deemed appropriate upon further exploration of the data during study implementation.

Demographics (last recorded)

- Age
- Sex
- Year of Cohort Entry
- Hospital Size (as a proxy for urban/rural).

Concomitant Medications

- Oral/Injected Corticosteroids
- Short acting beta agonist (SABA) (number of claims)
- Short acting muscarinic antagonist (SAMA) (number of claims)
- Systemic Xanthines
- Systemic Antileukotrienes
- Interleukin Inhibitors for Asthma
- Non-steroidal Respiratory Anti-inflammatories
- Opioids/Narcotics
- Systemic Antihistamines
- Oral Antibiotics for a Respiratory Condition (number of claims)
- Cough and Cold Preparations
- Diabetes Mellitus Medications, excluding Insulin
- Insulin
- Cytostatics
- Antirheumatics, Biologic
- Antirheumatics, Non-Steroidal
- Antithrombotic Agents
- Lipid-lowering Agents
- Antihypertensives/Diuretics
- Antiepileptics/Psycholeptics/Psychoanaleptics
- Antipsoriatics
- Antivirals
- Thyroid Therapies
- Vaccinations

[Antibiotics + Respiratory diagnosis, [REDACTED] can try to find antibiotics specific to respiratory conditions]

Comorbidities/Symptoms

- COPD Exacerbations (number of exacerbations)
- All-Cause Hospitalization
- Hospitalization due to Respiratory Condition
- Acute Myocardial Infarction, AMI
- Angina Pectoris
- Peripheral Vascular Disease, PVD
- Heart Failure, HF

- Hypertension
- Cardiac Arrhythmias
- Cerebrovascular Disease
- Any Cancer (except nonmelanoma skin cancer)
- Allergic Rhinitis
- Chronic Sinusitis
- Bronchiectasis
- Pneumonia
- Chronic Bronchitis

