9.6 DATA MANAGEMENT

Dataset

The Medical Data Vision dataset is comprised of administrative records of longitudinal inpatient, outpatient and drug data from multiple hospitals that have been standardized and de-identified prior to use for the analysis. The statistical analysis will be conducted using the

COPD Maintenance Therapy Drug Duration

Given limited information on treatment duration in the MDV data, a days supply of 14 days will be assumed for “Spiolto Respimat 28puffs.” Otherwise, 30 days will be assumed for all LAMA, LABA, and ICS maintenance therapies, including “Spiriva Inhalation Capsules 18microg”, “Spiriva 2.5microg Respimat 60puffs 150microg”, “Spiriva 1.25microg Respimat 60puffs 75microg”, and “Spiolto Respimat 60puffs”. A grace period of 14 days between assumed end of days supply and subsequent prescription will be used as an allowable gap.

Handling of Missing Data

Missing data that occurs in covariates or descriptive variables will be classified as its own level (i.e. missing data indicator). In addition, a feasibility assessment before beginning the

analyses will be done, and variables with >75 % missing values will be excluded from all analyses, other than baseline characteristics. If a variable is left with only one level other than missing, the variable will be excluded completely from all analyses.

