9.8 QUALITY CONTROL

The study protocol has been written following the Code of Conduct by the European Network of Centres for Pharmacoepidemiology and Pharmacovigilance (ENCePP) [R15-4870] that provides a set of rules and principles for post-authorization studies with regard to the best practices and

transparency, thereby promoting scientific independence of such studies. The study will be registered to the ENCePP's E-register and the results will also be published on the same site.

The study protocol also follows the key elements of the Guideline for Good Pharmacoepidemiology Practices (GPP) by International Society for Pharmacoepidemiology [R11-4318], and the recent draft Guidance for Industry and FDA Staff "Best Practices for Conducting and Reporting Pharmacoepidemiologic Safety Studies Using Electronic Healthcare Data Sets" [R15-4859]. The guidelines for good pharmacoepidemiology practices (GEP) in non-interventional studies will be respected along with any applicable local laws and regulations. This trial is not in the scope of Good Clinical Practice (GCP) studies.

██████████ will build measures for cohort inclusion, outcomes and covariates. Some of the measure algorithms will be based on those collaboratively developed for another respiratory-related protocol with clinical input from external pulmonology experts (i.e. ICD-10 code lists for comorbidities). Regarding medications, because the health claim coding system in MDV is unique to Japan and not well documented in academic articles, queries based on generic name/brand name will be used to determine the code list for each medication measure.

All measures created, cohorts developed, statistical analyses implemented, and tables completed will undergo quality control review by at least 1 additional analyst or scientist under the supervision of the Principal Scientist. Quality controls include checks for the validity and logical content of codes and checks for missing values and variables. In order to control for potential inconsistencies and errors, all variables will be tabulated. In addition, the distribution of each variable will be examined. Extreme observations with values larger than ± 3 standard deviations (SD) will be examined as potential outliers and consequently excluded from the dataset.

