This protocol will be strictly followed in the study. However, measure definitions may undergo modification if determined to be scientifically sensible. All changes to this protocol will be documented in protocol amendments.

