9.12 BIAS

In principle, electronic pharmacy dispensing records are considered accurate because pharmacists fill prescriptions with little room for interpretation, and are reimbursed by insurers based on detailed, complete, and accurate claims submitted electronically (Levy 2003; Sternbach 1988). Pharmacy dispensing information is usually seen as the gold standard of drug exposure information compared to self-reported information or prescribing records in medical records.

The population-based nature of the database will avoid selection bias and ensure external validity. Confounding bias through observable covariates will be controlled for by the design, which includes propensity score matching. Specifically, compared to traditional propensity

score matching, high dimensional propensity scores will be used to reduce overfitting while retaining baseline covariate balance in matched groups (**Schneeweiss 2009**).

To minimize misclassification of the recorded patient characteristics, previously validated algorithms or code lists will be used whenever available. Code lists will be reviewed by the qualified medical reviewers prior to implementation. Basic plausibility checks will be implemented for continuous variables (e.g. age, etc.).

The covariates chosen in [section 9.3.3](#) are hypothesized to be confounders in the relationship between exposure and outcome. The range and quantity of variables selected are aimed to make the two exposure groups more comparable so that the effect estimates may more readily have a causal interpretation.

COPD patients who start on Spiriva® Respimat® may be different than Spiolto® Respimat® initiators in the clinical course and severity of COPD. Use of propensity score matching aim to reduce bias due to confounding. The addition of covariates chosen by hDPS will further aid in reducing bias by empirically selecting for strong confounders. However, it is possible that inclusion of some variables may introduce rather than remove bias (i.e. as collider bias or M-bias). Nevertheless, such biases are demonstrated to be minor, and inclusion of variables preceding exposure are generally thought to improve rather than degrade validity (**Rassen 2011**).

The requirement of second fill for inclusion in the study could lead to immortal time bias. However, as the follow-up will begin after the second fill rather than at the cohort entry date, this requirement is unlikely to bias the findings.

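### The 3 SD exclusion rule in section 9.8 needs no evidence of error and does not exempt outcomes, so followed as written it drops genuine frequent exacerbators from the exacerbation-count analysis

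*Combined protocol and SAP*

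**What the plan says.** The rule closes the quality-control paragraph of section 9.8. Its scope is set just before: "In order to control for potential inconsistencies and errors, all variables will be tabulated. In addition, the distribution of each variable will be examined". Observations beyond ± "3 standard deviations (SD) will be examined as potential outliers and consequently excluded from the dataset".

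Other text that bears on it:

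- **Section 9.8, closing paragraph:** "This protocol will be strictly followed in the study". The latitude that follows concerns measure definitions, with changes documented by amendment.
- **Section 9.12:** "Basic plausibility checks will be implemented for continuous variables (e.g. age, etc".) No criterion is given, and the 3 SD exclusion is not tied to these checks.
- **Section 9.6:** "Missing data that occurs in covariates or descriptive variables will be classified as its own level (i.e. missing data indicator"). Outcomes are not mentioned.
- **Section 9.3.2.2:** "Number of Moderate or Severe COPD Exacerbations" is a secondary outcome. The number of respiratory hospitalisations is a further endpoint.
- **Section 9.3.3:** "COPD Exacerbations (number of exacerbations") is a baseline covariate and enters both propensity scores.
- **Section 9.2.1:** "Patients may have different lengths of follow-up (i.e. variable follow-up").

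None of the five sensitivity analyses in section 9.7.3 restores excluded observations.

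**The concern.** The paragraph sets out to catch errors, but the rule acts on distance from the mean alone. For a roughly symmetric measurement, 3 SD can be a reasonable flag for a recording error. For a zero-bounded, right-skewed count it is not: the lower limit is negative, so only high counts can be caught, and in COPD a high count can be a correctly recorded frequent exacerbator.

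Applied to follow-up counts, the rule selects patients on the outcome. Removing only the value rather than the patient does not help, because the missing-level rule in 9.6 does not reach outcomes and the high count still leaves the analysis. Because follow-up varies, a cut-off on raw counts also tends to remove the patients observed longest.

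Three choices are left open: the unit removed, a pooled or arm-specific SD, and whether screening comes before or after matching. Two analysts could follow the same sentence and analyse different datasets.

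**Working it through.** The plan states no figure for the effect of this rule and no mean or SD for exacerbation counts, so there is nothing to reproduce. The calculations below show what the rule does over assumed distributions.

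**Set-up.** The count has mean *m* and dispersion *d*:

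- variance = *m* + *d*·*m*² (*d* = 0 is Poisson)
- cut-off = *m* + 3·√variance; counts strictly above it are removed

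**1. Share removed, one group**

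Example with *m* = 0.5, *d* = 1:

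- Variance = 0.5 + 0.25 = 0.75, SD = 0.866. Cut-off = 0.5 + 3 × 0.866 = 3.10. The lower limit is −2.10, so it never binds.
- Patients with 4 or more events go. The probabilities of 0, 1, 2 and 3 events are 0.6667, 0.2222, 0.0741 and 0.0247, total 0.9877, so 1.2% of patients are removed.
- Mean events kept = 0.2222 + 2 × 0.0741 + 3 × 0.0247 = 0.444 of 0.5, so 11% of events are removed.

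Over a grid:

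| Assumed counts, mean 0.2 to 1.0 | Patients removed | Events removed |
|---|---|---|
| Negative binomial, *d* 1 to 4 | 1.0% to 4.4% (median 2.3%) | 10% to 52% (median 24%; middle 90% of grid 14% to 36%) |
| Poisson | 0.4% to 3.7% | 2% to 26% |

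The 52% end depends on where the cut-off falls between integers. At *m* = 0.2, *d* = 3.9 the cut-off is 1.99, so patients with 2 events go (4.1% of patients, 52% of events). At *d* = 4 it is exactly 2.00 and they stay (1.4% and 25%).

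**2. Two equal arms, true rate ratio 0.80, removed patients leaving the count analysis**

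Example with Tio mean 0.5, Tio/Olo mean 0.4, *d* = 2:

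- Variances: 0.5 + 2 × 0.25 = 1.00 and 0.4 + 2 × 0.16 = 0.72.
- *Pooled cut-off:* mean 0.45, variance (1.00 + 0.72)/2 + 0.05² = 0.8625, cut-off 0.45 + 3 × 0.929 = 3.24. Counts of 4 or more go in both arms: 2.2% of Tio and 1.3% of Tio/Olo. At 1,829 per arm, the most that 1:1 matching allows from section 9.5, that is about 41 and 24 patients. Remaining means are 0.401 and 0.342, ratio **0.853**. The difference falls from 0.100 to 0.059.
- *Arm-specific cut-offs:* Tio 0.5 + 3 × 1.00 = 3.50, Tio/Olo 0.4 + 3 × 0.849 = 2.95. Tio loses counts of 4 or more (2.2%), Tio/Olo loses counts of 3 or more (3.4%). Remaining means are 0.401 and 0.286, ratio **0.712**.

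| Grid | Pooled ratio | Fall in absolute difference (pooled) | Arm-specific ratio |
|---|---|---|---|
| Tio mean 0.5 to 1.0, *d* 2 to 4 | 0.85 to 0.89 | 38% to 65% | 0.71 to 0.88 |
| Tio mean 0.2 to 1.0, *d* 0 to 4 | 0.81 to 0.89 | 8% to 75% | 0.58 to 0.89 |

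When the arms have identical distributions the ratio stays at 1.00.

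**3. Variable follow-up**

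Follow-up is assumed uniform from 30 days (1 to 31 March 2019, the shortest possible in the section 9.2.1 timeline) to 3.5 years (28 September 2015 to 31 March 2019), with 0.2 to 0.8 events per year and *d* 0 to 2. Removed patients average 2.6 to 3.0 years of follow-up against 1.8 overall. The event rate is understated by 3% to 32%.

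**The case against.** The best reply is that the sentence closes a paragraph on code validity and data errors, and that values are to be examined first, which suggests judgement. On that reading it screens source variables and would not touch derived outcome counts. The context supports this intention, but the wording does not secure it: scope is every variable, exclusion is stated as the consequence, and no criterion for keeping a value is given.

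Other points stand as limits on the size, not on the defect:

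- Section 9.7 plans rates, risks and Cox regression only for triple therapy. No model or effect measure is given for exacerbation counts, so the rate ratio above is an assumed estimate.
- The wider two-arm grid shows that the distortion can be close to nil or larger than in the narrower one.
- Section 9.2.1 ends follow-up at triple therapy. If that also applies to the counts, frequent exacerbators who escalate stop accruing events, which could thin the tail. Enrolment ending at the last encounter also makes uniform follow-up a simplification. Neither effect can be sized from the documents.
- The commitment to follow the protocol strictly is qualified by freedom to modify measure definitions. An exclusion rule is not a measure definition, so this does not rescue it.

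**Conclusion.** The concern holds. That the rule lacks an error criterion, an exemption for outcomes and a defined unit of removal is certain from the text. That it removes high counts from the exacerbation analysis follows from its literal application and the shape of count data.

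The size is not known. Under the assumed distributions a few per cent of patients carry roughly a tenth to a half of the events, and absolute exacerbation rates are understated. If the arms truly differ, a pooled cut-off pulls the ratio towards 1. Arm-specific cut-offs can move it either way, so an unstated choice determines the direction.

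The demonstrated effect is confined to secondary and further count endpoints. Applied to baseline counts, the rule mainly restricts the cohort; bias in the matched comparison or the primary Cox analysis is possible but not shown. This should be fixed before the analysis is run.

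**What to change.** In section 9.8, delete the closing clause that orders exclusion and replace it with:

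> Flagged values of continuous or count variables are checked for plausibility. Only impossible or erroneous values are set to missing. All plausible values and all patients are kept. No patient is excluded on an outcome or post-entry variable. Numbers flagged and changed are reported by arm.

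The essential parts are the error criterion and the bar on excluding by outcome. Reporting by arm makes the handling visible. Optionally, if extreme baseline counts destabilise the propensity model, cap or categorise them in that model only.

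The cost is a few sentences, no new data and negligible analysis time.

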9.9 LIMITATIONS OF THE RESEARCH METHODS

This study will be conducted using hospital-based health insurance claims following the DPC payment system and is subject to certain limitations. One limitation is that these are based on a large, non-random convenience sample based in Japan, which may contain biases or lack generalizability to other populations. Data also come from a subset of hospitals in Japan, which would lead to failure to record events if patients visit medical centers not included in MDV's data sources (**Tanaka 2015**). Moreover, because healthcare is nationalized in Japan, the notion of enrolment is not applicable, and all patients are assumed to be observable throughout the global date range of the data. However, if a patient's emigration or mortality is not captured, then they would remain in the study despite not truly being eligible for any events, thereby leading underestimations of the risks and rates and possible bias in the hazard ratio if these patients are differentially distributed between the exposed and unexposed groups.

Another limitation of the study is that patients on monotherapy may escalate to double therapy before receiving the triple therapy. The patients starting on double therapy do not have this option. Therefore, patients on monotherapy may take longer to get to triple therapy than the patients on double therapy.

Additionally, the MDV database also poses some limitations inherent to prescription claims data. Electronic outpatient pharmacy dispensing records are considered accurate because pharmacists fill prescriptions with little room for interpretation and are reimbursed by the government on the basis of detailed, complete, and accurate claims submitted electronically (Sternbach 1988, Levy 2003). Pharmacy dispensing information is usually seen as the gold standard of drug exposure information compared to self-reported information (West 1995) or prescribing records in outpatient medical records (West 1994). However, claims data are subject to certain limitations. The presence of a claim for a filled prescription does not indicate that the medication was consumed or that it was taken as prescribed, and any medications filled over-the-counter or provided as samples by the physician will not be observed in the claims data. This concern is somewhat mitigated by requiring 2 claims within 60 days for cohort entry. Finally, patients are required not to have a claim for Tiotropium/Olodaterol or Tiotropium during the baseline period, but patients may have taken maintenance therapies prior to the start of the baseline period.

MDV database only captures in-patient deaths, and mortality, one of the secondary outcomes, maybe under-reported in the data. However, the magnitude of the underestimation is unlikely to differ by exposure and comparison cohorts.

In the analytical portion of this protocol, propensity score matching will be used to ultimately derive the causal parameters of interest. Many covariates are included in the prediction model of the propensity scores, but as with all non-interventional studies, the potential for unmeasured and residual confounding cannot be ruled out.

